Informed consent – study staff will obtain informed consent from interested individuals before they are discharged from the inpatient unit. The study staff member will review all study activities, emphasize that participation is voluntary, discuss potential risks and benefits of participating, and review the participant's responsibilities. An individual is considered enrolled once informed consent has been provided.

Post-consent activities and outcomes assessments

Outcome assessments are performed at three time points across an individual's participation in the study: baseline (while the participant is admitted to the inpatient unit), 3 months, and 6 months from their enrollment in the study.

Beck Hopelessness Scale, Beck Scale for Suicidal Ideation, Columbia Suicide Severity Rating Scale, State Hope Scale, Interpersonal Needs Questionnaire, Multidimensional Scale of Perceived Social Support, Meaning of Life Questionnaire, Single-Item Self Rating of Medication Adherence, NIH Adult Toolbox Social Relationship Scales, Patient Health Questionnaire (PHQ-9), Quality of Life Enjoyment and Satisfaction Questionnaire Short Form, Self-Efficacy to Avoid Suicidal Action Scale, Working Alliance Inventory – Client, Short Form 12, and health service utilization inventory (lifetime or 3 month interval) – these will be collected via self-reported measures at baseline, 3 month, and 6 month assessments.

Randomization and Blinding

Randomization will be conducted using a minimization algorithm implemented by the University of Michigan's Consulting for Statistics, Computing & Analytics Research (CSCAR) center.(80) The two variables included in the minimization are gender and whether the participant made a suicide attempt immediately prior to hospital admission. These variables were chosen to avoid the potential confounding that could arise if by chance these variables were not equally distributed during random assortment.(81) Randomization will be stratified by study site. After a participant has completed consent procedures and the baseline assessment, a research assistant will access the CSCAR web application, input the two variables, and receive the allocation assignment.

All follow-up assessments will be completed by a separate research assistant who will be blinded to study arm assignment.

Control & Experimental Interventions

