The primary outcome is to determine the effectiveness of the PREVAIL peer mentorship intervention for reducing suicide attempts and suicidal ideation among recently hospitalized adult psychiatric patients at high risk for suicide. In a two-site, randomized controlled trial (N=490), participants in the 3-month peer mentorship intervention arm will be less likely to report a suicide attempt on the Columbia Suicide Severity Rating Scale (CSSR-S) and will report less severe suicidal ideation on the Beck Scale for Suicidal Ideation (BSI) over the 6 months following enrollment compared to those in an enhanced usual care control condition.

1. Suicide attempts (measured by the Columbia Suicide Severity Rating Scale) [Time Frame: 6-months]
Any suicide attempt as measured according to an electronic self-report version of the Columbia Suicide Severity Rating Scale (CSSR-S). The definition of suicide attempt for the primary outcome will consist of any actual suicide attempt, aborted suicide attempt, or interrupted suicide attempt according to the CSSR-S.
2. Change in suicidal ideation (measured by the Beck Suicide Scale (BSS)) [Time Frame: Baseline, 6-months]
Patient's current suicidal ideation as measured by the Beck Suicide Scale (BSS). The BSS is a self-report 19-item scale preceded by five screening items. The BSS and its screening items assess thoughts, plans and intent to commit suicide. All 24 items are rated on a three-point scale (0 to 2). Total scores could range from 0 to 48 (if the screening items are included). No specific cut-off scores exist to classify severity. Increasing scores reflect greater suicide risk.

Secondary Outcomes

1. Medically serious suicide attempts (measured by the medical record) [Time Frame: 6-months]
Any suicide attempt as notated in the patients electronic medical record. The definition of suicide attempt for the primary outcome will consist of any actual suicide attempt, aborted suicide attempt, or interrupted suicide attempt.

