Based on our pilot study findings and those of other randomized controlled trials of psychosocial interventions that included suicide attempts as a primary outcome (91, 92, 109), we powered the study with the assumption that frequency of suicide attempts at 6 months will be 22% in the intervention arm vs. 36% in the control arm. We will enroll 490 patients in total, and assuming a 25% dropout rate, 368 (184 per group) will provide primary outcome data. The proposed sample size is expected to provide 84% power to detect the desired difference between the two groups based on a two-sided 0.05 level test. The estimate of effect is based on an assumption that the effect of PREVAIL will be similar to that reported in a trial of cognitive behavioral therapy for suicide among suicide attempters (N=120) where the re-attempt rate at 6 months was 25% among intervention recipients vs. 40% for controls. (91) Although there is no prior literature comparing the effects of peer support to psychotherapy on suicide-specific outcomes, two meta-analyses have concluded the effects of peer support on depression are similar to psychotherapy. (49, 51) Our estimate of effect is conservatively less than that found for brief psychodynamic interpersonal therapy, where in one trial (N=119) the self-harm rate at 6 months was 9% in the intervention arm compared to 28% for controls. (92) For the primary outcome of suicidal ideation according to the Beck Scale for Suicidal Ideation at 6 months and measures of hope and belongingness at 3 months (Aim 2), our sample of 368 will provide 90% power to detect a standardized effect size (Cohen's d) of .34. For the mediator analysis, the proposed sample size is expected to provide 80% power to detect a significant mediator assuming that the intervention explains about 2% of the variance of the mediator (corresponding to "small" effect based on Cohen's criteria), and about 7% of the variance of suicide ideation is explained by the mediator adjusting for the intervention effect, or vice versa based on joint significance testing for the mediation effect. (110)

Data Analysis

Baseline Analyses

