We will examine the randomization process to determine if there were any between-group differences at baseline, particularly in variables that are thought to be potentially associated with suicide attempts or ideation. T-tests or chi-square analyses, as appropriate, will be used to test for differences in the following baseline variables between study groups: age, severity of suicidal ideation prior to admission, burdensomeness, hope/hopelessness, and measures of belongingness. When there are significant differences in the distribution of these variables, they will be included as covariates in multivariable analyses. Balance is expected for sex and recent suicide attempt due to randomization by minimization.

Data Verification/Univariate Analyses: We will examine the distribution of all study variables for extreme values, missing data, variances, possible coding errors, skewness and whether or how to categorize skewed data. We will describe means (SD) for the continuous measures and frequencies of dichotomous outcomes by study group for each assessment time for the entire sample and for each of the study sites, separately.

Primary Outcome

Primary analyses will determine the effectiveness of PREVAIL in decreasing the risk of any suicide attempt and in decreasing suicidal ideation at 6 months post-randomization. Primary analytic cohort will be "intent to treat", such that all randomized participants will be included according to their original study arm assignment, regardless of whether they subsequently drop out of participation in the intervention. Secondary analyses will be conducted using a "per protocol" cohort where only participants who complete 6 or more peer encounters will be compared to those assigned to the EUC arm. We will evaluate predictors of compliance by defining 6 or more peer encounters as compliance and will also obtain complier average difference (a.k.a. complier average causal effect) assuming a balanced proportion of compliance between arms. The estimates of the three analytic cohorts (intent to treat, per protocol and compliance average difference) will provide more robust understanding of the effect of PREVAIL. (106)

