Bivariate/Multivariate Analyses: To test for intervention effects at 6 months on the primary outcomes, a logistic regression model will be used for the dichotomous outcome of suicide attempt (as assessed by CSSR-S) and a multiple regression model will be used for suicidal ideation (as assessed by BSI). Each model will include the study arm as the primary predictor and will also include study site, gender, and prior suicide attempt, which were the balancing variables used in randomization. We will also adjust for additional covariates that show imbalances in baseline analyses. Outcomes at 6

[figure not shown]
months post-randomization will be our primary analysis in order to assess whether the intervention has lasting effects, but we will also assess immediate effects at 3 months using similar analytic approaches.

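### Two primary outcomes, each planned at the full two-sided 0.05, have no decision rule linking them; if either can carry the claim, familywise error is about 9.1–9.8%

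*Combined protocol and SAP*

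**What the plan says.** Under Primary Outcomes, the protocol describes a single aim: "The primary outcome is to determine the effectiveness of the PREVAIL peer mentorship intervention for reducing suicide attempts and suicidal ideation". It then numbers attempts (Columbia scale) and ideation (Beck scale) as primary outcomes 1 and 2. The hypothesis is directional: "participants in the 3-month peer mentorship intervention arm will be less likely to report a suicide attempt", with less severe ideation joined to it by a plain conjunction.

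The Statistical Analyses Plan repeats the pair under Primary Outcome: "Primary analyses will determine the effectiveness of PREVAIL in decreasing the risk of any suicide attempt and in decreasing suicidal ideation". It makes 6 months and intention-to-treat primary. Under Bivariate/Multivariate Analyses each outcome has a separate model: "To test for intervention effects at 6 months on the primary outcomes, a logistic regression model will be used" for attempts, and a multiple regression for ideation.

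Under Sample Size, attempts set the trial's size: "we powered the study with the assumption that frequency of suicide attempts at 6 months will be 22% in the intervention arm", against 36% in the control arm, with "84% power to detect the desired difference between the two groups based on a two-sided 0.05 level test". Ideation is also called primary there, but it receives only a detectable effect, d = 0.34, shared with the Aim 2 measures: "measures of hope and belongingness at 3 months (Aim 2), our sample of 368 will provide 90% power to detect a standardized effect size". No significance level is restated for it.

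The text available for review contains no both-or-either rule, testing order, division of alpha or other multiplicity adjustment for these two outcomes.

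**The concern.** One verdict on effectiveness rests on two tests, and the plan does not say how they combine. The same data can therefore give different verdicts. Take attempts p = 0.04 and ideation p = 0.20:

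| Rule | Verdict |
|---|---|
| Either suffices, each at 0.05 | Positive, on attempts |
| Attempts first, then ideation | Positive for attempts only |
| Both required | Negative |
| Hochberg | No claim; adjusted p = min(2 × 0.04, 0.20) = 0.08 for attempts |

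With the two p-values exchanged, only the either-suffices rule is positive. If the rule is chosen after the results are known, the claim can rest on whichever outcome reached 0.05. The verdict has practical weight: the protocol's background says that state-level training of peer specialists would start at once if the intervention proved effective.

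**Working it through.** **Inputs.** From Sample Size: 490 enrolled, 25% dropout, 368 analysed (490 × 0.75 = 367.5), 184 per arm; attempts 22% v 36%; ideation d = 0.34; two-sided 0.05, written for attempts. The documents give neither the correlation between the two test statistics nor an expected d for ideation, so both are assumptions here.

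**1. Reproduce the stated powers.**

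Attempts, pooled-variance test, mean proportion (0.22 + 0.36)/2 = 0.29:
- SE under the null = √(2 × 0.29 × 0.71/184) = 0.0473.
- SE under the alternative = √((0.36 × 0.64 + 0.22 × 0.78)/184) = 0.0467.
- At 0.05: Φ((0.14 − 1.960 × 0.0473)/0.0467) = Φ(1.01) = 84.4%. The plan states 84%.
- At 0.025 (critical value 2.241): 76.6%.

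Ideation, noncentral t on 366 df:
- Noncentrality = 0.34 × √(184/2) = 3.26.
- At 0.05: 90.2%. The plan states 90%.
- At 0.025: 84.3%.

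Both stated figures therefore match the full two-sided 0.05. This rules out an even split of alpha. It does not separate the remaining rules, because a both-required rule and a fixed sequence also test each outcome at 0.05.

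**2. Error if either outcome suffices.** With independent tests, two-sided familywise error is 1 − 0.95² = 9.75%, and the chance of a false benefit claim is 1 − 0.975² = 4.94%. With correlation, from bivariate normal statistics and a critical value of 1.96:

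| Correlation | Two-sided familywise error | False benefit claim |
|---|---|---|
| 0 | 9.75% | 4.94% |
| 0.2 | 9.64% | 4.84% |
| 0.4 | 9.32% | 4.66% |
| 0.5 | 9.07% | 4.54% |
| 0.7 | 8.35% | 4.17% |

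The comparators for one test are 5% and 2.5%.

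**3. Error and power under three controlling rules.** Noncentralities are 1.96 + 1.01 = 2.97 for attempts and 3.26 for ideation at d = 0.34.

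- *Hochberg at two-sided 0.05.* Familywise error is 5.0% to 4.8% and false benefit 2.56% to 2.40% (correlation 0 to 0.5). If both effects are real, power is 83.7% to 83.1% for attempts and 89.4% to 88.4% for ideation (correlation 0 to 0.6). If only that effect is real, it is about 77% for attempts and 85% for ideation.
- *Attempts first, then ideation.* No inflation. Power for attempts stays at 84.4%. If only ideation responds, ideation can be claimed only when attempts reach significance by chance, about 2.3–2.5% of the time.
- *Both required.* No inflation. Joint power at d = 0.34 is 76.2%, 78.3% and 79.8% at correlation 0, 0.4 and 0.6. At d = 0.30 it is 69–74%, and at d = 0.25 it is 57–63%.

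**The case against.** The documents lean towards attempts as the lead outcome. The title names attempts alone, the background section on intervention mechanisms describes Aim 1 as concerning attempts, the sample size is built on attempts, and attempts are listed first. The conjunction in the hypothesis could also mean that both outcomes must succeed. Under either reading there is no inflation, and the reproduced powers fit both. It can also be argued that two separately reported claims, each with its own 2.5% error for benefit, need no joint control.

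Much of this stands. A reader might infer that the plan runs at nearly 10% type I error, or that the sponsor means to claim success on whichever test is significant. The documents support neither inference: the inflation belongs to one reading, and the plan never adopts it.

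The gap itself remains. Ideation is called primary under Primary Outcomes, in Sample Size and in the analysis section, so the lean towards attempts is not a hierarchy. The conjunction states a hypothesis and does not set a condition for success; if it were the rule, 84% and 90% would not be the power of the success criterion, and the joint power is unreported. The separate-claims view sits poorly with a single effectiveness determination and would itself need to be stated.

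**Conclusion.** The concern holds as a missing decision rule, worth fixing before outcomes are compared by arm. Its size is conditional. If either outcome can carry the claim, two-sided familywise error is about 9.1–9.8% and the chance of a false benefit claim about 4.5–4.9%, for an assumed correlation of 0 to 0.5; at 0.7 both remain well above the one-test values. If both are required or attempts go first, error is held, but power for the actual success criterion or for ideation differs from what is printed. These figures cover only the two 6-month primary tests. The full 0.05 for ideation is inferred from its power figure, and d = 0.34 is used as an assumption because the plan gives it only as a detectable effect.

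**What to change.** Add one rule to the SAP and restate power to match. The plan describes blinding only for follow-up assessors ("All follow-up assessments will be completed by a separate research assistant who will be blinded to study arm assignment"), so the deadline is best set as the first comparison of outcomes by arm.

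**Default, Hochberg.** Suggested text: *The two primary outcomes at 6 months are tested by Hochberg's procedure at two-sided 0.05. Both are claimed if both p-values are at most 0.05; otherwise only an outcome with p at most 0.025 is claimed. Benefit is claimed only if the estimate favours PREVAIL.* Label d = 0.34 as an assumption when stating power.

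**Acceptable alternatives, at the sponsor's choice.**
- A fixed sequence, attempts then ideation. This fits the title, the description of Aim 1 and the sample-size basis, and keeps 84% for attempts. It gives up almost any chance of claiming an effect on ideation alone.
- A both-required rule, with joint power of about 76–80% stated (d = 0.34, correlation 0 to 0.6).

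**If comparative data have already been seen,** report both outcomes with Hochberg-adjusted p-values and say that the rule was set afterwards.

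**Cost.** One SAP paragraph and no more patients. Under Hochberg, a lone p-value between 0.025 and 0.05 no longer supports a claim. At d = 0.34 power falls by about 1–2 points if both effects are real and 5–7 points if only one is. At d = 0.25 the loss is larger: up to 4 points for attempts if both are real, and about 10 points for ideation if only ideation responds (67% to 57%).

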Peer providers will be hired for the study from the pool of those already trained in the intervention during the R34, and new peer providers will be recruited with the assistance of the director of peer specialist training in the State of Michigan, [name], who maintains a database of all state-trained peer specialists. [name] served on the expert panel that developed the PREVAIL intervention, assisted with hiring during the R34, and will continue to support the project throughout the R01 (see Letter of Support). [name] will facilitate recruitment of peer specialists for the study via direct personal contacts and e-mail announcements to peer specialists who reside in or near Washtenaw and Oakland Counties. In order to allow participants the opportunity to choose from among several PREVAIL peer mentors, we will hire 6 to 8 peer providers with diverse backgrounds to deliver the intervention on a part-time hourly basis. We do not anticipate difficulty hiring peer providers based on our experience during the R34 and with other peer support research trials.

Concomitant Treatment

Contamination of the EUC group would most likely occur via receipt of non-study sources of peer support. We will exclude participants who are currently receiving or intending to receive either individual peer mentorship from a Certified Peer Support Specialist, or group-based, suicide prevention-focused peer support, on a biweekly or more frequent basis outside of the study, and will measure non-study peer support via the adapted Health Services Inventory measure. (87) Indirect contamination could occur via communication between PREVAIL and EUC participants while on the inpatient unit, though any such occurrences are expected to be of minor significance relative to the subsequent greater dose of peer mentorship received by PREVAIL participants.

Allowed Interventions

Once a participant is enrolled into the study, there is no restriction on the types of other care they may receive during their participation. If a participant is assigned to the peer mentorship intervention arm, study staff will send a letter to the participant's outpatient mental health provider informing them that the patient will be receiving peer mentorship as part of this study.

Prohibited Interventions

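### Intervention participants are nested within a planned 6 to 8 peer mentors and controls are not; the stated 84% and 90% power and the primary standard errors hold only if mentor clustering is nil or mentors are treated as fixed

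*Combined protocol and SAP*

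**What the plan says.** Study Interventions, Delivery and Duration: "we will hire 6 to 8 peer providers with diverse backgrounds to deliver the intervention". Under Delivery of Treatment, each intervention participant picks one mentor from short self-written descriptions and then meets that mentor. The enhanced usual care arm receives a caring message and has no mentor.

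Sample Size: "We will enroll 490 patients in total", with 25% dropout leaving 368, or 184 per group. The assumption is that the "frequency of suicide attempts at 6 months will be 22% in the intervention arm vs. 36% in the control arm", giving "84% power to detect the desired difference between the two groups", "based on a two-sided 0.05 level test". For ideation at 6 months, and for hope and belongingness at 3 months, the same 368 give "90% power to detect a standardized effect size (Cohen's d) of .34". No number of mentors, ICC or design effect enters.

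Bivariate/Multivariate Analyses: "Each model will include the study arm as the primary predictor and will also include study site, gender, and prior suicide attempt". Covariates imbalanced at baseline are added. There is no mentor term and no cluster-robust variance. The only random effect in the plan is the participant intercept under Effects over time, which handles repeated measures within a person and not participants who share a mentor. Approach to Missing Data adds nothing on this point.

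**The concern.** The design is partially nested: outcomes may be correlated within mentor in one arm only. The protocol itself gives reasons to expect mentors to differ. They are hired for diverse backgrounds, session content is deliberately flexible and chosen by the mentor, the mentor's own recovery story is a core ingredient, and fidelity is sampled mentor by mentor.

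With about 23 to 31 analysed participants per mentor, a small ICC matters. If mentors are regarded as a sample from the peer workforce, the intervention-arm mean carries between-mentor variance that the planned models leave out. Confidence intervals would then be too narrow for a claim about peer mentorship in general. That is the claim the protocol intends, because the background sections describe wide use by certified peer specialists if the intervention proves effective.

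**Working it through.** **Inputs.** From Sample Size: 184 analysed per arm; 22% v 36%; d = 0.34; two-sided alpha 0.05. From Delivery and Duration: 6 to 8 mentors. Assumed: equal caseloads, so m = 184/8 = 23 or 184/6 = 30.7; mentor ICC from 0 to 0.05, because the documents give none; normal critical values.

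**Step 1: reproduce the plan.**
- Attempts, pooled normal test. The mean rate is (0.22 + 0.36)/2 = 0.29. Null SE = sqrt(2 x 0.29 x 0.71/184) = 0.0473. Alternative SE = sqrt((0.22 x 0.78 + 0.36 x 0.64)/184) = 0.0467. Power = Phi((0.14 - 1.96 x 0.0473)/0.0467) = 84.4%.
- Ideation: SE = sqrt(2/184) = 0.1043. Power = Phi(0.34/0.1043 - 1.96) = 90.3%.

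Both stated figures are therefore arithmetically right, and both are the independence case.

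**Step 2: add nesting in the intervention arm only.** Design effect DE = 1 + (m - 1) x ICC multiplies that arm's variance; the control variance is unchanged.
- Attempts: null SE = sqrt(0.29 x 0.71 x (DE + 1)/184); alternative SE = sqrt((0.22 x 0.78 x DE + 0.36 x 0.64)/184).
- Ideation: SE = sqrt((DE + 1)/184).
- Example, 8 mentors at ICC 0.05: DE = 1 + 22 x 0.05 = 2.10. Attempts: null SE 0.0589, alternative SE 0.0567, power = Phi((0.14 - 1.96 x 0.0589)/0.0567) = 67%. Ideation: SE 0.1298, power = Phi(0.34/0.1298 - 1.96) = 75%.

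**Step 3: type I error of the unadjusted test, mentors random.** The ratio of true to model SE under the null is sqrt((DE + 1)/2), and the error rate is 2 x (1 - Phi(1.96/ratio)). Example: sqrt(3.10/2) = 1.245, which gives 11.5%.

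| ICC | Mentors | DE | Attempt power | Ideation power | SE ratio | Type I error |
|---|---|---|---|---|---|---|
| 0 | either | 1.00 | 84% | 90% | 1.000 | 5.0% |
| 0.01 | 8 | 1.22 | 81% | 87% | 1.054 | 6.3% |
| 0.01 | 6 | 1.30 | 79% | 86% | 1.072 | 6.7% |
| 0.02 | 8 | 1.44 | 77% | 84% | 1.105 | 7.6% |
| 0.02 | 6 | 1.59 | 75% | 82% | 1.139 | 8.5% |
| 0.05 | 8 | 2.10 | 67% | 75% | 1.245 | 11.5% |
| 0.05 | 6 | 2.48 | 62% | 70% | 1.320 | 13.8% |

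A t reference with Satterthwaite degrees of freedom, as few mentors require, lowers power further. At ICC 0.05, attempts / ideation become 64.9% / 68.8% with 8 mentors and 57.6% / 60.5% with 6 (unpooled variance for attempts).

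**Step 4: when the type I error column applies.** In a null simulation of a continuous outcome (184 per arm, 8 mentors, between-mentor variance 5% of the total), the unadjusted test rejected 11.4% of the time when mentors were redrawn at random for each trial. It rejected 5.0% of the time with fixed mentor effects averaging zero, and 4.8% when similar participants merely chose the same mentor. The inflation therefore needs mentors that are random and have real effects on outcome.

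**The case against.** A reader might infer that the power statement is wrong as written, or that the primary tests will exceed 5% because participants choose their mentors. The documents support neither reading. They give no ICC, and the 84% and 90% reproduce exactly under independence. Participants are randomised individually and choose a mentor only after allocation, so sorting of similar people onto the same mentor makes the arm mean no more variable. If mentorship affects nobody, mentors cannot differ in effect. If inference is confined to this panel of mentors, the unadjusted test is valid. These limits stand, and the point is conditional on them.

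Other features may keep the ICC small. Weekly group supervision, fidelity rating of 20% of sessions and a common risk protocol standardise delivery. The primary endpoint falls at 6 months, after a 3-month intervention. In the pilot, encounters averaged 5.6 (SD 4.8) and 9 participants had none after discharge, which dilutes an intention-to-treat ICC. The 6 to 8 is a hiring plan for part-time staff over 3 years of recruitment. With turnover to 12 mentors and ICC 0.01, DE = 1 + (184/12 - 1) x 0.01 = 1.14 and attempt power is 82%. If mentors are tied to a site, the site covariate absorbs part of their variance. Against this, caseloads made unequal by choice and availability would raise the design effect. None of these features fixes the ICC at zero.

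The pilot remark that poor engagement was not specific to individual mentors concerns engagement, not outcome. It rests on 4 mentors and is not offered as a reason for independence.

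**Conclusion.** The concern holds conditionally. The plan omits a one-arm clustering that its own design creates. For any positive mentor ICC with mentors taken as random, the primary standard errors are too small and the stated power is too favourable. Over an assumed ICC of 0.01 to 0.05 with equal caseloads, attempt power runs from 81% to 67% (8 mentors) or 79% to 62% (6 mentors), and ideation power from 87% to 75% or 86% to 70%. The corresponding type I error is about 6-7% rising to 12-14%. The direction is firm; the size is not, because it rests on an ICC that the documents do not give. Treating mentors as random is reasonable here because the stated goal is use by the wider peer workforce. The documents do not show that the sample size was miscalculated or that the primary result will be invalid for the mentors in this trial. This is an inexpensive improvement to the plan rather than a correction of an error.

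**What to change.** Keep the models under Bivariate/Multivariate Analyses as primary. Add one pre-specified sensitivity analysis per primary outcome: the same covariates, plus a mentor random effect in the intervention arm only. Define mentor as the one first selected, so that switches and non-starters stay in the intention-to-treat set.

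- Ideation: linear mixed model with Satterthwaite or Kenward-Roger degrees of freedom.
- Attempts: a risk-difference (linear) version with the same correction, because a logistic variance component from 6 to 8 mentors is poorly estimated.
- Reporting: give the mentor ICC with its interval beside each primary result. If significance does not survive, qualify any generalisation beyond the study mentors.
- Sample Size: state that 84% and 90% assume no mentor clustering, and give the range over ICC 0 to 0.05.

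The cost is plan wording and two extra models. The mentor selected is already known at assignment, so no new data, staff or enrolment are needed. The downsides are wider intervals, an imprecise ICC from few mentors and a less favourable stated power. Pre-specifying matters, because a mentor adjustment chosen after the results are seen would be open to challenge.
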